2.1. Study Rationale

This Phase 3 study will evaluate the efficacy and safety of once-weekly administration of LY3209590 on glycemic control compared with daily administration of insulin degludec in insulin naïve adult participants with T2D who are starting basal insulin therapy for the first time. This study will inform the clinical development of LY3209590.

2.2. Background

Current state of diabetes care

Most people with diabetes are not achieving glycemic targets. Treatment complexity, fear of hypoglycemia, delays in insulin initiation and intensification, and suboptimal dosing may pose challenges to diabetes care. There is a need to overcome barriers to dose optimization with basal insulins that provide simple dosing algorithms, rapid achievement of glycemic targets, and a predictable profile with low likelihood of contributing to hypoglycemia.

Potential for improved treatment regimens and compliance

Once-weekly insulin with a simple titration regimen could result in earlier adoption of insulin therapy that may improve treatment compliance and lead to better real-world patient outcomes. Weekly insulins with a lower peak-to-trough profile during the week and a nearly flat insulin profile could also reduce within-day glucose variability and result in more consistent and predictable glycemic control.

LY3209590

LY3209590 is a novel insulin receptor agonist that is in development as a once-weekly basal insulin for the treatment of hyperglycemia in patients with T2D and T1D. LY3209590 has the potential to decrease patient burden, overcome barriers to initiation of insulin therapy, and may improve glycemic control and quality of life for these patients.

A detailed description of the chemistry, pharmacology, nonclinical and clinical efficacy, and safety of LY3209590 is provided in the IB.

Summary of clinical results

A total of 5 clinical studies, in healthy participants and participants with T2D, have been completed to assess the PK/PD, safety, and efficacy of LY3209590. The results thus far support continued development of LY3209590 as a treatment for diabetes mellitus.

Phase 1 results

LY3209590 pharmacokinetics show a low peak-to-trough ratio and extended half-life that supports once-weekly dosing.

Single-ascending doses of LY3209590 lowered fasting glucose in a dose- and concentration-dependent manner, with a prolonged time-action profile.

Overall, LY3209590 was well tolerated in healthy participants and participants with T2D.

Phase 2 Study BDCL preliminary results

Study BDCL is a randomized, open-label, comparator-controlled study evaluating the efficacy and safety of LY3209590 compared with insulin degludec. Study participants have T2D, are insulin naïve, and treated with a stable dose of metformin, alone or in combination with a stable dose of a DPP-4 inhibitor and/or an SGLT2 inhibitor, for at least 3 months prior to screening.

Safety data during 26 weeks of treatment in participants with T2D showed no increased risk of safety with LY3209590 compared to degludec.

LY3209590 was noninferior to degludec for glycemic control as measured by change in HbA1c after 26 weeks of treatment.

2.3. Benefit/Risk Assessment

Detailed information about the known and expected benefits and risks and reasonably expected adverse events of LY3209590 may be found in the IB, and that of insulin degludec may be found in the local product package insert.

2.3.1. Risk Assessment

Potential risks for this study

The potential risks associated with LY3209590 include

- hypoglycemia
- hyperglycemia
- hypersensitivity reaction
- injection site reactions, for example, injection site rash, erythema, or pruritus or lipohypertrophy
- immunogenicity, and
- cardiovascular risks.

It is expected that the known risks would be similar to other insulins.

Safety data available to date suggest that there is no increased risk to participants' safety with LY3209590 treatment compared to insulin degludec.

Potential risks for the LY3209590-prefilled pen device are described in the "Instructions for Use".

Management of Risks

Sections [5.1](#), [5.2](#), [6.1.2](#), [6.8.1](#), and [8.3](#) address known potential risks associated with LY3209590.

Protocol risk management measures***Participant education for hypoglycemia***

After signing informed consent, all participants will be educated about signs and symptoms of hypoglycemia, how to treat hypoglycemia, and how to collect appropriate information for each episode of hypoglycemia. Hypoglycemia may be identified by spontaneous reporting of symptoms from participants, whether confirmed or unconfirmed by simultaneous glucose values, or by blood glucose samples collected between study visits.

Monitoring of participant blood glucose levels

Each participant will have a study-provided glucometer that will wirelessly transfer participant SMBG to their study-provided e-diary. Participants should use the glucometer whenever hypoglycemia is experienced or suspected and check glucose values.

A web-interface and reporting system will be available for use by study personnel to view participant e-diary entries, including SMBG, insulin doses, and hypoglycemia information throughout the study. Automated alerts will be transmitted to the investigator any time the participant reports a potential severe episode of hypoglycemia, defined as requiring assistance due to neurological impairment, in the e-diary.

Dose modification and rescue therapy

The dosing algorithm used in the study requires consideration and adjustment of insulin dosing by the investigator based on participant FBG and hypoglycemia events (see Section 6.5).

Participants will be monitored for persistent, severe hyperglycemia and will receive rescue therapy if this should occur (see Section 6.1.2).

2.3.2. Benefit Assessment

Participants may benefit by receiving personal health information, routine safety assessments, and frequent engagement with health care providers during the study, which provide opportunities for coaching and support.

Participants may also benefit from the improvement of glycemic control promoted by basal insulin. The weekly administration of LY3209590 has the potential to offer a more consistent glycemic control.

2.3.3. Overall Benefit Risk Conclusion

Considering the clinical data to date and measures taken to minimize risk for the participants in this study, the potential risks identified in association with LY3209590 are justified by the anticipated benefits that may be afforded to insulin naïve participants with T2D.

3. Objectives, Endpoints, and Estimands

Objectives	Endpoints
Primary	
Demonstrate noninferiority of LY3209590 compared to insulin degludec for the treatment of T2D in adults	Change in HbA1c from baseline to Week 52
Key Secondary (Multiplicity Adjusted)	
Demonstrate noninferiority of LY3209590 compared to insulin degludec for participants using GLP-1 receptor agonists	Change in HbA1c from baseline to Week 52
Demonstrate noninferiority of LY3209590 compared to insulin degludec for participants not using GLP-1 receptor agonists	Change in HbA1c from baseline to Week 52
Demonstrate superiority of LY3209590 compared to insulin degludec in selected parameters of glycemic control	
 Change in HbA1c from baseline to Week 52 Time in glucose range between 70 and 180 mg/dL (3.9 and 10.0 mmol/L), inclusive, collected during the CGM session prior to Week 52
Other Secondary	
Compare the effect of LY3209590 to insulin degludec in parameters of glycemic control	
 Change from baseline to Week 26 of HbA1c Time in glucose range between 70 and 180 mg/dL (3.9 and 10.0 mmol/L), inclusive, collected during the CGM session prior to Week 26 Change from baseline to Weeks 26 and 52 of fasting glucose measured by SMBG Glucose variability measured during the CGM session prior to Weeks 26 and 52 Insulin dose at Weeks 26 and 52

Compare the effect of LY3209590 to insulin degludec on safety endpoints	
 Incidence and rate of composite of Level 2 and 3 hypoglycemia events during the treatment period Incidence and rate of composite of Level 2 and 3 nocturnal hypoglycemia events during the treatment period Change from baseline to Weeks 26 and 52 in body weight Measurements collected during CGM sessions prior to Weeks 12, 26, and 52 of 
 Time in hypoglycemia with glucose <70 mg/dL (3.9 mmol/L) Time in hypoglycemia with glucose <54 mg/dL (3.0 mmol/L) Time in hyperglycemia defined as glucose >180 mg/dL (10.0 mmol/L)
Compare the effect of LY3209590 to insulin degludec on patient-reported outcomes questionnaires	
 Change from baseline to Weeks 26 and 52 of 
 TRIM-D SF-36, and EQ-5D-5L
Tertiary	
Compare the effect of LY3209590 to insulin degludec in participants using GLP-1 receptor agonists versus participants not using GLP-1 receptor agonists	
 Rate of Level 1 and composite of Level 2 and 3 hypoglycemia events during the treatment period Change from baseline to Weeks 26 and 52 in body weight Insulin dose at Weeks 26 and 52 Measurements collected during CGM sessions prior to Weeks 12, 26, and 52 of 
 Time in hypoglycemia with glucose <70 mg/dL (3.9 mmol/L) Time in hypoglycemia with glucose <54 mg/dL (3.0 mmol/L) Time in hyperglycemia defined as glucose >180 mg/dL (10.0 mmol/L), and Time in glucose range between 70 and 180 mg/dL (3.9 and 10.0 mmol/L), inclusive

Compare the effect of LY3209590 to insulin degludec for efficacy parameters	
 Percentage of participants at Week 52 achieving 
 HbA1c <7% HbA1c <7% without nocturnal hypoglycemia, and HbA1c ≤6.5% without hypoglycemia Change from baseline to Weeks 26 and 52 of fasting serum glucose
Compare the effect of LY3209590 to insulin degludec for safety parameters	
 Incidence and rate of Level 2 hypoglycemia events during treatment period Incidence and rate of Level 3 hypoglycemia events during treatment period Evaluation of immunogenicity - incidence of positive LY3209590 treatment-emergent antidrug antibodies
Characterize the PK/PD of LY3209590	
 LY3209590 PK and concentration-response relationships to key safety and efficacy measures
Compare the effect of LY3209590 to insulin degludec for patient-reported outcomes	
 SIM-Q and Frequency of responses to Basal Insulin Experience of “likelihood of incorporating into routine”

Abbreviations: CGM = continuous glucose monitoring; GLP-1 = glucagon-like peptide-1; HbA1c = hemoglobin A1c; PK/PD = pharmacokinetics/pharmacodynamics; SMBG = self-monitoring of blood glucose; SF-36 = Short Form-36 Version 2 Health Survey Acute Form; SIM-Q = Simplicity Questionnaire; T2D = type 2 diabetes; TRIM-D = Treatment-Related Impact Measure – Diabetes.

Primary estimand

United States registration

The primary clinical question of interest is

What is the treatment difference between LY3209590 and insulin degludec in HbA1c change from baseline after 52 weeks of treatment, in study eligible participants, regardless of treatment discontinuation for any reason and regardless of initiation of rescue medication?

Treatment regimen estimand attributes

This table describes the treatment regimen estimand attributes.

Treatment Regimen Estimand Attribute	Description
Population	Targeted study population. See Section 9.2 for details.
Endpoint	HbA1c change from baseline to Week 52.
Remaining intercurrent events	None. The 2 intercurrent events, treatment discontinuation for any reason and initiation of rescue medication, are both addressed by the treatment condition of interest attribute.
Treatment condition	The randomized treatment regardless of treatment discontinuation and use of rescue medications.
Population-level summary	Difference in mean changes between treatment conditions.

Rationale for the treatment regimen estimand

The treatment regimen estimand estimates how participants with T2D are treated in clinical practice and considers both efficacy and safety.

Registration for countries outside the United States

The primary clinical question of interest is

What is the treatment difference between LY3209590 and insulin degludec in HbA1c change from baseline after 52 weeks of treatment, in study eligible participants who adhere to the randomized treatment without intercurrent events during the study treatment period?

Efficacy estimand attributes

This table describes the efficacy estimand attributes.

Efficacy Regimen Estimand Attribute	Description
Population	Targeted study population. See Section 9.2 for details.
Endpoint	HbA1c change from baseline to Week 52.
Remaining intercurrent events	None. The 2 intercurrent events, treatment discontinuation for any reason and initiation of rescue medication, are both handled by the hypothetical strategy, for example, the potential outcome for those participants if the intercurrent events have not occurred will be estimated.
Treatment condition	The randomized treatment.
Population-level summary	Difference in mean changes between treatment conditions.

Rationale for the efficacy estimand

The efficacy estimand supports the interpretation of the treatment effect as participants adhere to study treatment and free from the confounding effect of rescue medications.

Secondary estimands for multiplicity-adjusted objectives

The superiority test in change from baseline to Visit 31 (Week 52) in HbA1c will also be based on the primary estimands described above.

The change from baseline to Visit 31 (Week 52) in HbA1c in the subpopulations of participants using or not using GLP-1 receptor agonists will use treatment regimen estimand for US registration and efficacy estimand for other countries.

The time in glucose range between 70 and 180 mg/dL (3.9 and 10.0 mmol/L) inclusive measured during CGM session prior to Visit 31 (Week 52) will use treatment regimen estimated for US registration and efficacy estimand for other countries.

4. Study Design

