9.5. Sample Size Determination

Approximately 888 participants will be randomly assigned to LY3209590 and insulin degludec in a 1:1 ratio. With the assumption of 15% dropout at Week 52, approximately 377 and 377 participants will complete 52 weeks of treatment on LY3209590 and insulin degludec, respectively.

The primary objective of this study is to test the hypothesis that LY3209590 is noninferior to insulin degludec on glycemic control as measured by change from baseline to Visit 31 (Week 52) in HbA1c in participants with T2D who are starting basal insulin for the first time. 754 completers (377 on LY3209590 and 377 on insulin degludec) will provide an at least 99% statistical power to show noninferiority between LY3209590 and insulin degludec using the upper limit of a 2-sided 95% confidence interval (LY3209590 – insulin degludec) and these assumptions

- NIM of 0.4%
- no true difference between treatment groups, and
- an SD of 1.1%.

This sample size also has at least 95% statistical power to show noninferiority between LY3209590 and insulin degludec using a 0.3% NIM at Week 52.

The number of participants in each subpopulation of background treatment will be approximately 50% of the study population with balanced treatment assignment to support the following secondary objectives, controlled for Type 1 error:

To demonstrate noninferiority of LY3209590 to insulin degludec in HbA1c change from baseline to Week 52 for the subpopulation of participants using GLP-1 RAs

To demonstrate noninferiority of LY3209590 to insulin degludec in HbA1c change from baseline to Week 52 for the subpopulation of participants not using GLP-1 RAs.

In each subpopulation, 188 completers for each study intervention will provide an approximately 90% statistical power to show noninferiority between LY3209590 and insulin degludec using the upper limit of a 2-sided 95% confidence interval (LY3209590 – insulin degludec) and these assumptions

- a NIM of 0.4%
- no true difference between treatment groups, and
- an SD of 1.1%.

The 754 completers will provide 95% statistical power to demonstrate the superiority of LY3209590 versus insulin degludec, of change in HbA1c from baseline to 52 weeks, assuming an SD of 1.1% and true mean difference is -0.3%, using the alpha of 0.05.

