CGM parameters (treatment regimen estimand)	The baseline will be derived from the data collected during CGM session prior to the first dose date of study treatment. Multiple imputation will be used to impute missing observations at baseline.	The CGM session prior to Visit 24 (Week 26) and Visit 31 (Week 52) in EAS1 Multiple imputation approach will be used to impute missing observations at Visit 24 (Week 26) and Visit 31 (Week 52).
CGM parameters (efficacy estimand)	The baseline will be derived from the data collected during CGM session prior to the first dose date of study treatment.	The CGM sessions prior to Visit 7, 15, 24, and 31 (Weeks 4, 12, 26, and 52) in EAS2 for MMRM

Analysis	Baseline Observations	Post-Baseline Observations
Insulin dose during the treatment period	N/A	
All scheduled visits between Visit 3 and Visit 31 in EAS2 for MMRM.
 
The averages of weekly basal insulin doses between visits for individual participants will be used in the analysis. (Section 4.4.2.1)

Fasting glucose by SMBG	
The baseline period is the lead-in period up to the day of first dose of study treatment. Baseline will be derived as the average of all fasting glucose measurements between V2 date and the first dose date.
 
Multiple imputation will be used to impute missing observations at baseline for treatment regimen estimand.
	
All available data after the day of first dose of study treatment up to Week 52 (Visit 31) in EAS2 for MMRM (efficacy estimand).
 
Values at each visit will be derived as average of all fasting glucose measurements from the day post prior visit up to the day of next visit.
 
Data at Week 26 (Visit 24) and Week 52 (Visit 31) in EAS1 for ANCOVA with multiple imputation for missing data (treatment regimen estimand).

Fasting serum glucose	
The baseline is the last non-missing assessment prior to or on the day of the first dose of study treatment.
 
Multiple imputation will be used to impute missing observations at baseline for treatment regimen estimand.
	
All scheduled visits after the day of first dose up to Week 52 (Visit 31) in EAS2 for MMRM (efficacy estimand)
 
Planned measurements at scheduled visits will be included.
 
Data at Week 26 (Visit 24) and Week 52 (Visit 31) in EAS1 for ANCOVA with multiple imputation for missing data (treatment regimen estimand)
 
.

Analysis	Baseline Observations	Post-Baseline Observations

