4.3.2. Main analytical approach

The primary objective is to test the hypothesis that LY3209590 is noninferior to insulin degludec on glycemic control in the targeted study population. The noninferiority test will be based on either of the 2 estimands: **treatment regimen estimand** for the US FDA submission and **efficacy estimand** for registrations in other countries. The full significance level of 0.05 will be used for each estimand.

The following table provides the details of treatment regimen estimand and efficacy estimand.

	Treatment Regimen Estimand	Efficacy Estimand
Analysis Population	All participants in EAS1 with non-missing baseline measure	All participants in EAS2 with non-missing baseline measure and at least one non-missing post-baseline scheduled measure
Analysis Data	All non-missing observations at baseline and Week 52 (Visit 31) regardless of the use of study intervention or rescue medications.	All non-missing observations at baseline and all scheduled post-baseline timepoints during treatment period (that is, Weeks 2, 4, 12, 16, 26, 36 and 52) (prior to the date of last study dose + 10 days for LY3209590 (+1 day for degludec), or the initiation of rescue medication whichever is earlier for participants with intercurrent events).
Missing Data	There may be missing values at Week 52 (Visit 31) due to early study discontinuation. The missing values will be imputed using multiple imputation by the retrieved dropout approach. The retrieved dropout participants are those who discontinue study intervention prior to Week 52 but have non-missing measures at Week 52 in the same treatment arm. If there are only a limited number of retrieved participants that leads to a failure in performing the multiple imputation analysis, such as the model cannot converge, or the number of retrieved dropout participants is small (i.e., at least 1 arm has <8 participants who discontinued study treatment early and have endpoint visit measurements), the missing HbA1c at Week 52 will be imputed by return-to-baseline multiple imputation approach (Qu and Dai 2022)	There may be missing values due to the early discontinuation of study intervention or use of rescue medication. The MMRM model will be used, and the missing values will be handled in the MMRM analysis under the assumption of missing at random.

	Treatment Regimen Estimand	Efficacy Estimand

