4.4.1.2. Main analytical approach

The non-inferiority test in change from baseline to Week 52 (Visit 31) in HbA1c for each of the subpopulations with participants using or not using GLP-1 RA will be analyzed. For the treatment regimen estimand (using data from the EAS1), for each subpopulation, the missing data will be imputed by multiple imputation with the approach similar to the imputation used for the primary endpoint. The imputed data for that subpopulation will be analyzed by the ANCOVA model using treatment, strata (country and SU use at randomization), and baseline HbA1c as independent variables. For the efficacy estimand (using data from the EAS2), the MMRM model which includes treatment, strata (country and SU use at randomization), visit and treatment-by-visit interaction as fixed effects, and baseline HbA1c as a covariate will be used, with data from that subpopulation.

The superiority test in change from baseline to Week 52 (Visit 31) in HbA1c will be based on the same primary endpoint analysis described in Section [4.3.2](#).

The time in glucose range between 70 and 180 mg/dL inclusive measured by CGM will be analyzed using an ANCOVA model for treatment regimen estimand and an MMRM model for efficacy estimand. CGM Primary Analysis Population will be used for the analyses. The analyses are similar to the primary analysis described in Section 4.3.2 with additional term of baseline HbA1c stratum ($<8.0\%$, $\geq 8.0\%$) in analysis models. For treatment regimen estimand, only participants with an observation at baseline or at Week 52 will be included in the analysis. the missing data at Week 52 will be imputed by multiple imputation with the approach similar to the imputation used for the primary endpoint. The missing baseline will be imputed using multiple imputation under assumption of missing at random.

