4.4.2. Supportive secondary Endpoint(s)

4.4.2.1. Other Efficacy Endpoints

The analysis of change from baseline for HbA1c at Week 26, fasting glucose by SMBG at Week 26 and 52, CGM (except for variability) parameters at Week 26 and 52 will be performed for both treatment regimen estimand and efficacy estimand. The analyses for other supportive efficacy endpoints will be based on the EAS2 data.

For treatment regimen estimand, only participants with an observation at baseline or at the endpoint visit will be included in the analysis. The missing baseline will be imputed using multiple imputation under assumption of missing at random. Missing data at the endpoint visit will be imputed using either retrieved dropout or return-to-baseline multiple imputation approach determined by the criterion described for the primary efficacy endpoint in Section 4.3.2. ANCOVA analysis will be conducted similar to that for the primary endpoint. An additional term of baseline HbA1c stratum ($<8.0\%$, $\geq 8.0\%$) will be added into the model for the endpoints other than HbA1c.

For efficacy estimand, participants with baseline and at least one post baseline observation will be included in the analysis. The longitudinal observations of actual and change from baseline in HbA1c to Week 26 will be analyzed using the same MMRM model as for the efficacy estimand described in Section 4.3.2. The analyses of other continuous efficacy measures (fasting glucose, insulin dose and CGM parameters) will use an MMRM model similar to that for the primary endpoint with an additional term of baseline HbA1c stratum ($<8.0\%$, $\geq 8.0\%$). The variance-covariance structure in the MMRM models for fasting glucose from SMBG and insulin dose will be based on compound symmetry.

Longitudinal logistic regression model with baseline value, strata (country, GLP-1 use at randomization, SU use at randomization and baseline HbA1c stratum [$<8.0\%$, $\geq 8.0\%$]), Treatment, Time, and Treatment-by-time interaction as factors will be used for analysis for CGM targets of glycemic control. See Section 4.3.2 for variance-covariance structure selection.

The time point for primary CGM data analysis is CGM session. In addition, the average time in glucose range, hypoglycemia range and hyperglycemia range by week (by visit for treatment period) will be summarized by treatment. Average daily time within each range since last dose

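### For CGM endpoints, the efficacy-estimand analysis excludes participants with no valid baseline session, while the treatment-regimen analysis imputes that baseline. The cost is precision, not bias

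*Protocol*

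**What the plan says.** Protocol Section 3 (secondary estimands for multiplicity-adjusted objectives) only assigns the estimands: time in range "measured during CGM session prior to Visit 31 (Week 52) will use treatment regimen estimated for US registration and efficacy estimand for other countries". The missing-baseline rules are in the SAP.

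- **Treatment regimen estimand.** In the CGM row of the SAP 4.1 table: "Multiple imputation will be used to impute missing observations at baseline". SAP 4.4.1.2 repeats this for time in range, under missing at random, with an inclusion condition: "For treatment regimen estimand, only participants with an observation at baseline or at Week 52 will be included in the analysis".
- **Efficacy estimand.** The matching row of the SAP 4.1 table has no imputation sentence. SAP 4.4.1.2 describes the time-in-range analyses as similar to those of 4.3.2, where the efficacy-estimand population is "All participants in EAS2 with non-missing baseline measure and at least one non-missing post-baseline scheduled measure". For CGM parameters more generally, SAP 4.4.2.1 states: "For efficacy estimand, participants with baseline and at least one post baseline observation will be included in the analysis".

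Protocol 9.3.3.1 specifies an MMRM with baseline as a covariate and does not mention a missing baseline. EAS2 itself (Protocol 9.2, SAP Section 3) has no baseline CGM condition.

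**The concern.** Under the efficacy estimand, a participant without a valid two-week lead-in session is removed even if the sessions before Weeks 4, 12, 26 and 52 are all valid. Outcome data are discarded for want of a covariate that the same SAP imputes for the other estimand.

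Neither estimand explains the difference. The only intercurrent events are treatment discontinuation and rescue, and a failed lead-in session is neither.

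The rule comes from HbA1c, whose baseline is a central laboratory value. A CGM baseline also has to pass the validity rule in SAP Appendix 6: at least three valid days within a visit, each with at least 70% of expected readings. At stake is the precision of a multiplicity-controlled superiority test used outside the US, and of the other CGM endpoints under the same rule.

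**Working it through.** **Inputs from the documents (Protocol 9.5).** Planned enrolment is 888, split equally (444 per arm). On completion, the plan states: "With the assumption of 15% dropout at Week 52, approximately 377 and 377 participants will complete 52 weeks of treatment". For time in range: SD 18%, true difference 5%, alpha 0.05 (two-sided per SAP 4.1), stated power at least 95% with 754 completers.

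**Assumptions.** The share f with no valid baseline session is not given; 5-20% is used. The baseline-to-Week-52 correlation ρ is not given; 0.4-0.6 is used.

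**1. Reproduce the stated power.**
- SE = 18 × √(2/377) = 1.311.
- Power = Φ(5/1.311 − 1.96) = Φ(1.854) = 96.8%, which agrees with at least 95%.

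**2. Find the break-even loss.** For 95% power, n = 2 × (1.960 + 1.645)² × 18² / 5² ≈ 337 per arm. The tolerable loss is 1 − 337/377 = 10.6%.

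**3. Upper bound on the harm.** Treat each lost participant as fully informative, so n = 377(1 − f) and the SE is multiplied by 1/√(1 − f).

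| f | n per arm | SE increase | Power |
|---|---|---|---|
| 0 | 377 | – | 96.8% |
| 5% | 358 | 2.6% | 96.1% |
| 10% | 339 | 5.4% | 95.1% |
| 20% | 302 | 11.8% | 92.7% |

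**4. What keeping them recovers.** A participant without a baseline has outcome variance σ², against σ²(1 − ρ²) for one with a baseline, and so carries 1 − ρ² as much information. The gain relative to the current analysis is f(1 − ρ²)/(1 − f).
- f = 10%: 0.111 × 0.64 = 7.1% (ρ = 0.6) to 0.111 × 0.84 = 9.3% (ρ = 0.4). The SE without the fix is larger by √1.071 − 1 = 3.5% to √1.093 − 1 = 4.6%.
- f = 20%: 0.25 × 0.64 = 16% to 0.25 × 0.84 = 21%. The SE is larger by √1.16 − 1 = 7.7% to √1.21 − 1 = 10%.

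This formula weights each participant by his or her own residual variance. A model with one pooled residual variance recovers somewhat less. Filling the baseline from correlated pre-randomization measures recovers somewhat more.

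**5. Check whether planned analyses cover it.** SAP 4.4.1.3 only adds inadvertently enrolled participants. Appendix 6 plans an analysis on all CGM data for selected, unnamed parameters. That could restore a baseline lost to the validity rule, but not one that was never recorded.

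**The case against.** **The loss may be negligible.** The validity rule is lenient for a two-week session, participants are trained at Visit 2, and sites re-educate when session compliance falls below 80% (Protocol 8.1.1.2). The share affected may be small. Protocol 9.5 also does not say whether the 18% SD is adjusted for baseline. If it is unadjusted, adjustment multiplies the SE by √(1 − ρ²), or 0.917 at ρ = 0.4. A 20% loss then gives 1.118 × 0.917 = 1.025, an SE of 1.344 and power Φ(5/1.344 − 1.96) ≈ 96%. This stands: the size is unknown and power is probably adequate. It does not explain why the two estimands are treated differently.

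**The imputation sentence in SAP 4.4.1.2 might cover both estimands.** It follows sentences about the treatment regimen estimand. Read as covering both, it would conflict with the 4.1 table and 4.4.2.1, so the text would still need correcting.

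**Stronger readings that the documents do not support:**
- *Bias.* A reader might infer that dropping participants biases the test. The baseline session precedes the first dose, so conditioning on it should not by itself distort the randomized comparison.
- *Wrong population.* A reader might infer that the ex-US test fails to cover its stated population. The estimand table's entry, "Targeted study population. See Section 9.2 for details", is for HbA1c, and SAP 4.3.2 openly defines the narrower analysis set. The CGM Primary Analysis Population (Dexcom G6 users) already leaves out China under both estimands. A missing covariate is a missing-data matter.
- *Treatment-regimen inclusion rule.* A reader might also want to delete the condition in "For treatment regimen estimand, only participants with an observation at baseline or at Week 52 will be included in the analysis". With 10% missing baselines and 15% missing Week 52 (assumptions), it excludes about 888 × 0.10 × 0.15 ≈ 13 participants. Keeping them means imputing both values, which is awkward under the return-to-baseline fallback. That is not a clear gain.

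**Conclusion.** The point holds as one of efficiency and consistency. For CGM endpoints analysed under both estimands, a missing baseline is imputed for one and leads to exclusion for the other. For time in range at Week 52, the efficacy-estimand exclusion is inherited from SAP 4.3.2 through 4.4.1.2; SAP 4.4.2.1 states it directly for the other CGM parameters.

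The recoverable precision is modest: about 3.5-4.6% of the SE if 10% lack a valid baseline and about 8-10% if 20% do. The 5.4% and 11.8% in step 3 are upper bounds, because they count each lost participant as fully informative. On that same basis the stated 95% power is at risk only above about 10.6% loss. All of this rests on an assumed missing share and correlation. The change is worth making because it recovers data already collected at little cost.

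**What to change.** In SAP 4.1, 4.4.1.2 and 4.4.2.1, state that efficacy-estimand CGM analyses include every participant in both EAS2 and the CGM Primary Analysis Population who has at least one valid post-baseline session. Fill a missing baseline from pre-randomization data only, by the same rule in both arms; screening HbA1c and lead-in fasting SMBG are candidates. Keep the protocol's MMRM with baseline as a covariate, so the protocol model does not change. Leave the treatment-regimen inclusion rule as it is.

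The cost is some SAP wording, a little programming and an assumption about missing baselines that the SAP already accepts for the other estimand. If multiple imputation is used for the fill, add repeated MMRM fits and Rubin's combination; a single fill rule based only on pre-randomization data avoids that.
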